#### 4.1.3 Method of assigning patients to treatment groups

During visit 2, eligible patients in both study parts will be randomised to receive 12 weeks of treatment (i.e. three administrations) with Placebo or either of the two (part 2) or three (part 1) active dose regimens at equal distribution and stratified according to previous BIO experience (TNF-AND-Vedo versus TNF-OR-Vedo), and concomitant corticosteroid therapy at visit 2/randomization (yes/no). In addition, a stratification for Japan versus non-Japan will be done in order to assure that sufficient patients per treatment group are recruited specifically to support individual country submission in Japan; this strata will be treated as an operational strata and will not be included into the analyses of the primary endpoint. In order to limit the proportion of last-line-treatment patients, screening of both TNF-AND-Vedo failure patients will be capped once 48 randomized patients in Part 1 and 117 randomized patients in Part 2 meet this criterion; the patients who have been already screened at time of implementation of the cap will continue screening procedures in preparation for randomization into the study. The assignment and capping of enrolment into the TNF-AND-Vedo stratum will be done via Interactive Response Technology (IRT).

Details regarding the use of the IRT are described in the site-user manual available in the ISF.

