### 5.2.2 Vital signs

Vital signs evaluations will be performed at visits as shown in the [Flow Chart](#). This includes temperature, pulse rate, systolic/diastolic blood pressure and respiratory rate. Respiratory rate, pulse rate, and blood pressure will be measured after patients have been sitting comfortably for at least five minutes. Measurement of vital signs should precede blood sampling to avoid the impact of blood sampling on the vital measurements. At dosing visits (Visits 2, 4 and 5) vital signs evaluations will be performed pre-dose and additional evaluations will be taken approximately at 5 minutes post-dose and 60 minutes post-dose.

Patients should be closely monitored for signs and symptoms of hypersensitivity reactions for approximately 2 hours after the first dose administered and 1 hour following all other doses of study drug. Hypersensitivity reactions should be treated according to medical standards. Pre-medications for further injections might be considered and will be agreed on between investigator and BI clinical monitor.

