B.01	Informed consent not available/not done LABEL: Informed consent not available	Based on direct assessment, not simply the tick box (which is A1.09). Date of informed consent missing or no signature on patient's "Declaration of Informed Consent" In this case: Patient's data will be removed from database and not be used at all.	All analyses #
B.02	Informed consent too late LABEL: Informed consent too late	Informed consent date was after Visit 1, i.e., after any screening procedure	None

Table 6.2: 1 (cont'd) Handling of iPDs

Category / Code	Description	Comments	Excluded from ¹
C	Trial medication and randomisation		
C1	Incorrect trial medication		
C1.01	Incorrect medication received by patients in Placebo arm	
Placebo patient who received ≥ 1 vial (150mg) of BI 655130 verum overall /at any dosing visit
 
Can only be finally judged after DBL since unblinding information is required
	PPS
C1.02	Incorrect medication received by patients in BI arms	
BI patient who received BI dose not matching treatment that was randomized would be considered an iPD.
 
BI 655130 treated patient who fulfils any of the following:
 
For 300mg SD patients,
 
 received ≥ 1 vial (150mg) of BI 655130 verum different from planned at any visit 
For 450mg q4w patients,
 
 received any 2 vials (300mg) of BI 655130 verum different from planned at any visit or overall 
For 1200mg q4w patients,
 
 received any 3 vials (450mg) of BI 655130 verum different from planned at any visit or overall 
Can only be finally judged after DBL since unblinding information is required
	PPS

Table 6.2: 1 (cont'd) Handling of iPDs

Category / Code	Description	Comments	Excluded from ¹
C2	Non-compliance		
C2.01	Non-compliance with study drug intake – administered dose too low	Administered overall infusion volume is less than 80% of the total planned volume (except that infusion is interrupted due to safety concerns, as described in CTP section 4.1.4). The total planned volume is 
 • 100mL if discontinuation before visit V2 • 100 mL at each visit (200mL total) if discontinuation before V4 • 100 mL at each visit (300mL total) if discontinuation before V5 The total planned volume overall is 300 mL.	PPS
C2.02	Wrong treatment schedule	Patient received treatment 2 weeks outside scheduled time.	PPS
C3	Randomisation not followed		

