D2.04	Concurrent UC treatments need to be on stable doses prior or up to Week 12: Probiotics (e.g. S. boulardii) LABEL: Probiotics not stable	Medical review	None	#
F	Study specific analysis			
F1	Other trial specific violation			
F1.01	Incomplete diagnosis of ulcerative colitis LABEL: Incomplete diagnosis of UC	Medical review	PPS	#
F1.02	Primary endpoint assessment more than 2 weeks before planned day LABEL: Primary endpoint assessment > 2 weeks before planned.		PPS	
F2	Certain violations of procedures used to measure primary or secondary efficacy data	<not specified>		
G	Other safety related violations			
G1.01	Pregnancy test not done for woman of child bearing potential, or pregnant during study LABEL: Pregnancy test not done or pregnant	Pregnancy test not done at any visit where such is scheduled	None	

PV will be detected manually

For specification on definition of analysis sets, refer to Section 6.3. Analysis of efficacy data according to the PPS will be done at the time of the 2nd interim database snapshot only [including all randomized patients through week 12].

Source: BI reference document 'Identify and Manage Important Protocol Deviations (iPD)' [001-MCS-50-413] (4, 6).

¹ See [Section 6.3](#) for population definition

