6.3 SUBJECT SETS ANALYSED

From CTP Section 7.3:

There will be 4 main patient populations in this trial for analyses: the randomized set (RS), the safety analysis set (SAF), the modified RS (m-RS), and the per-protocol set (PPS).

Randomized Set (RS)

This patient set includes all randomized patients. Treatment assignment will be as randomized. This is the main analysis set for presentation of efficacy on binary endpoints.

Safety Analysis Set (SAF)

This patient set includes all patients who were randomized and received at least one dose of study drug. It will be the main analysis set for presentation of safety. Patients will be analyzed according to the actual treatment.

Modified Randomized Set (m-RS)

This patient set includes all patients in the RS who had a baseline and at least one post-baseline measurement for the endpoint under consideration. Treatment assignment will be as randomized. This is the main analysis set for presentation of efficacy on continuous data, e.g. IBDQ.

Per-Protocol Set (PPS)

This patient set includes all patients in the RS who adhered to the CTP without any iPDs (potentially affecting the study outcome) which lead to exclusion from the PPS. This set will be used for sensitivity analysis on the primary efficacy endpoint.

In addition, the following patient sets will be defined for analysis.

Enrolled set (ES)

This patient set includes all patients who signed informed consent. It will be used for analyses of patient disposition.

For the first interim database snapshot, modified versions of the ES, RS, SAF, and m-RS will be defined: the ES_i, RS_i, the SAF_i, and the m-RS_i. Each of the modified patient sets will include those patients from the original set who completed/discontinued through the week 12 visit on or prior to the cut-off date (see Section 3). Each of these modified patient sets will be handled according to the same procedures used to derive the full patient sets.

For the analyses to be performed at the time of the second interim database snapshot (when all randomized patients have completed/discontinued through week 12), and at the time of the final, updated trial analysis, the ES, RS, SAF, m-RS, and PPS will be used. Corresponding

analyses performed at the time of the first interim database snapshot will use the ESi, RSi, SAFi, and m-RSi.

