7.3 TREATMENT COMPLIANCE

Only descriptive statistics are planned for this section of the report.

Treatment compliance will be summarised overall and by visit via total volume infused (as a % of planned) for the RS using descriptive statistics (N, mean, SD, minimum, median, maximum). The volume infused (as a % of planned) is defined as the volume infused at a visit (in ml as recorded in the eCRF), divided by 100 ml (the volume the patient should have received), times 100. If at least 100 mL has been infused, then it is assumed that the full planned dose has been administered, i.e. compliance is 100%.

For the patients who discontinued the study treatment prematurely, only the scheduled visits before premature discontinuation will be used for the calculation of overall compliance.

The number and percentage of patients with the following overall compliance categories will be presented:

- "<50% of planned",
- "50 to <80% of planned"
- "80 to 100% of planned".

The number of patients who received a dose will also be tabulated per visit.

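### Deviation rule C2.01 sets the planned infusion volume one infusion too high for patients who stop before V4 or V5, so fully infused early stoppers leave the per-protocol set although SAP 7.3 scores them 100%

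*SAP*

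**What the plan says.** SAP 6.2, Table 6.2: 1, code C2.01 covers under-dosing. The deviation is met, with exclusion from the PPS, when the overall infused volume is below 80% of the total planned volume. Infusions interrupted for safety as described in Protocol 4.1.4 are excepted. The planned total depends on when the patient stopped: 100 mL for a stop before V2, then "100 mL at each visit (200mL total) if discontinuation before V4" and "100 mL at each visit (300mL total) if discontinuation before V5". For the full course, "The total planned volume overall is 300 mL".

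The dosing schedule is stated elsewhere. Protocol 5.2.2: "At dosing visits (Visits 2, 4 and 5) vital signs evaluations will be performed pre-dose". Protocol 4.1.3 gives the same number of infusions in every arm: "12 weeks of treatment (i.e. three administrations) with Placebo" or an active regimen. Under Protocol 3.3.4.1, patients who stop study drug get no further infusions.

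SAP 7.3 defines compliance against 100 mL per dosing visit and, for patients who stop early, says that "only the scheduled visits before premature discontinuation will be used for the calculation of overall compliance".

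On the PPS, SAP 6.3 says: "This set will be used for sensitivity analysis on the primary efficacy endpoint". The footnote to Table 6.2: 1 adds: "Analysis of efficacy data according to the PPS will be done at the time of the 2nd interim database snapshot only".

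**The concern.** C2.01 and SAP 7.3 measure the same thing for the same patients with different denominators. C2.01 also conflicts with itself: a patient who stops before V5 is given the same 300 mL plan as one who was due all three infusions.

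Read literally, the rule labels as under-dosed, and drops from the PPS, patients who missed no infusion that was due to them. The deviation table would then list patients whom the compliance table shows at 100%.

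The exclusion is unlikely to be neutral. Codes D1.01 and D2.01 to D2.03 do not count medication given as rescue as a deviation. Protocol 4.2.1, however, stops study drug when a patient needs such treatment for worsening disease. A rescue user who stops before V5 is therefore spared by the D codes and removed by C2.01. Patients who stop because their disease worsens are plausibly less likely to remit, so removing them can move the PPS estimate, and by different amounts in different arms.

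**Working it through.** **Inputs.** Infusions at V2, V4 and V5 only (Protocol 5.2.2); three per patient in all arms (Protocol 4.1.3); 100 mL each (SAP 7.3); none after stopping (Protocol 3.3.4.1); exclusion limit 80% (C2.01).

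**Step 1: reproduce the planned totals.** Planned volume = 100 mL × number of dosing visits before the stop.

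| Stop | Stated in C2.01 | Due before the stop |
|---|---|---|
| before V2 | 100 mL | 0 mL |
| before V4 | 200 mL | 100 mL |
| before V5 | 300 mL | 200 mL |
| full course | 300 mL | 300 mL |

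Only the full course is reproduced. Counting V3 as if it were a dosing visit gives 0, 200, 300 and 400 mL, which fails for V2 and for the full course. Counting the named visit itself, that is, a stop at or after it, gives 100, 200, 300 and 300 mL and matches every line. The totals are thus shifted by exactly one infusion relative to the word 'before'.

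**Step 2: score a fully infused early stopper.** Compliance = infused / planned.

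| Stop | C2.01 | SAP 7.3 |
|---|---|---|
| before V4 | 100/200 = 50% | 100/100 = 100% |
| before V5 | 200/300 = 66.7% | 200/200 = 100% |

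The 80% floors under C2.01 are 0.8 × 200 = 160 mL and 0.8 × 300 = 240 mL. Both exceed what was scheduled by then (100 mL and 200 mL), so no such patient can pass without the exception.

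**Step 3: possible effect on the PPS (illustrative).** The documents give no discontinuation rate. Assume a share d of each arm is wrongly excluded, with d from 5% to 25%. Take remission rates p of 0.15 on placebo and 0.35 on active (base case, Protocol 7.7.1), a difference of 0.200. Let q be the remission rate among those excluded. Then PPS rate = (p − d·q)/(1 − d).

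| Excluded, placebo / active | Difference if q = 0 | Difference if q = p/2 |
|---|---|---|
| 25% / 5% | 0.368 − 0.200 = 0.168 | 0.359 − 0.175 = 0.184 |
| 5% / 5% | 0.368 − 0.158 = 0.211 | 0.205 |
| 15% / 15% | 0.412 − 0.176 = 0.235 | 0.218 |
| 25% / 25% | 0.467 − 0.200 = 0.267 | 0.233 |
| 5% / 25% | 0.467 − 0.158 = 0.309 | 0.408 − 0.154 = 0.254 |

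Differences are taken before rounding. With q = p the difference stays at 0.200. At the planned 40 per arm, 5% to 25% is 40 × 0.05 = 2 to 40 × 0.25 = 10 patients per arm.

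**The case against.** The strongest reply is that the volumes are sound and only the word 'before' is wrong: if each line means a stop at or after the named visit, all four totals are right. That is a likely origin of the error, but it confirms that the text is wrong, and code written from the text would misclassify patients. The V2 line has the same shift. It does no harm there: a patient with no infusion scores 0/100 = 0%, so no fully infused patient is misclassified.

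A second reply is that SAP 7.3 is descriptive and need not share a denominator with a PPS rule, and that excluding patients who had one or two of three infusions is a defensible per-protocol choice. It could be, but the SAP states no such intent and the tiers do not fit it: if the target were always 300 mL, there would be no reason to tier by time of stopping.

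Third, deviations are assessed for importance (SAP 6.2) and set membership is discussed at the database lock meeting (SAP 6.3). C2.01 does not carry the mark for manual detection, but codes C1.01 and C1.02 lack it too and still await a final judgement. So the review might catch the problem. A pre-specified rule should not depend on that.

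Three limits stand. The D codes do not promise that rescue users stay in the PPS, so the tension with C2.01 is one of effect and not a formal contradiction. The extremes in Step 3 need a fivefold imbalance between arms and no remission among those excluded. And some of these patients would leave the PPS anyway under F1.02, which covers a primary endpoint assessment more than two weeks early.

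**Conclusion.** The concern holds. On two lines, C2.01 sets the planned volume one infusion too high. Fully infused patients who stop before V4 or V5 score 50% or 66.7%, fall below 80% and leave the PPS, while SAP 7.3 scores them 100%. This follows from the documents alone.

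The severity is minor. Only the deviation table and one sensitivity analysis, run at the second interim snapshot, are affected. The primary analysis (randomized set, non-response imputation, MCP-Mod) and the 0.16 criterion are not.

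The size of the shift cannot be determined. The range of 0.168 to 0.309 around 0.200 rests on an assumed 5% to 25% wrongly excluded per arm, all non-remitters; it narrows to 0.184 to 0.254 if they remit at half their arm's rate and vanishes if they remit at the full rate. Overlap with F1.02 would reduce it. Arms may also be smaller than 40, because SAP Section 3 reports early termination.

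**What to change.** Align the V4 and V5 lines of C2.01 with SAP 7.3. The total planned volume should be:

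- 100 mL if treatment stops after the V2 infusion and before V4;
- 200 mL if it stops after the V4 infusion and before V5;
- 300 mL if all three infusions were due.

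The V2 line can stay as it is. The 80% floors become 80 mL, 160 mL and 240 mL, and fully infused early stoppers no longer meet C2.01. This changes an analysis denominator, not any dosing rule. The cost is two lines of SAP wording and one derivation, with no extra data or patients.

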### 3. DESCRIPTION OF DESIGN AND TRIAL POPULATION

#### 3.1 OVERALL TRIAL DESIGN AND PLAN

This is a multi-national, randomised, parallel-group, double-blind, phase II/III trial of BI655130 (SPESOLIMAB) in moderate to severe ulcerative colitis. This trial will investigate and confirm the efficacy and safety of 12 weeks of induction treatment with different dose regimens of BI655130 (SPESOLIMAB) in patients with moderate-to-severe ulcerative colitis who have failed previous biologic treatments in the past.

The trial comprises two distinct parts with different objectives, but with identical study populations, study endpoints and visit schedules. Two of the three BI655130 (SPESOLIMAB) regimens tested in Part 1 or a dose of 750mg q4w will be selected based on pre-defined decision criteria for confirmatory testing in part 2, but will not exceed the highest dose tested in part 1. The advantage of the operationally seamless design for the trial sites is the longer recruitment window, which will allow to enrol more patients, and to gain experience with the protocol measures. The anticipated shortened duration between end of the first trial part and start of the next will reduce the risk of measurement errors and protocol violations within Part 2, the confirmatory part of the trial. The overall expectation is therefore an increase in both site efficiency as well as the quality of the study. In addition, the increased experience with protocol measures is expected to lead to a reduction in the variability associated with efficacy measurements thereby increasing the precision of treatment estimates particularly in the confirmatory part, Part 2, of the trial. Finally, the accelerated recruitment compared to two separate trials may reduce time to availability of a new drug potentially filling a high unmet medical need in this population of patients.

A schematic overview of trial design is shown in Figure 3.1:1.

Figure 3.1:1 Trial Design

[figure not shown]

Table 3.1:1 Study definitions

Rescue Treatment	New or increase in dose of any medication, or a surgical procedure, applied to treat new or worsening symptoms related to ulcerative colitis
Disease worsening	Worsening of clinical status or symptoms of ulcerative colitis requiring administration of rescue medication in the investigator's opinion – in patients without a clinical response

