## 4.2 OTHER TREATMENTS, EMERGENCY PROCEDURES, RESTRICTIONS

### 4.2.1 Other treatments and emergency procedures

If the patient requires additional medical therapy or dose increase of baseline ulcerative colitis medication to treat the underlying ulcerative colitis due to disease worsening (cf. [Table 3.1.1](#) Study Definitions), the study drug must be discontinued and patients may receive conventional treatment for active disease. Such patients should stay in the trial but will be considered as treatment failures in the intent-to-treat (ITT) analysis.

If infusion or anaphylactic reaction had already occurred in the very same patient in the past, pre-treatment with steroids before next IMP administration is permitted as secondary prophylaxis.

Systemic steroids dosed intravenously or orally for less than 24 hours as treatment of infusion or anaphylactic reactions are permitted and do not lead to treatment discontinuation nor to assignment as treatment failures in the ITT analysis.

Management of Adverse Events:

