5.4.5 Rescue treatment

According to the definition of rescue treatment in CTP Section 3.1, rescue treatment includes:

- Newly administered medications or surgical therapy used to treat the underlying disease UC due to disease worsening or a disease flare

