C3.01	Treated without randomisation LABEL: Treated without randomisation	Patient treated according to eCRF, but not randomised according to IVRS.	RS(i), m-RS(i), PPS, SAF(i)
C3.02	Randomisation order not followed LABEL: Randomisation order not followed/stratification error	Stratification error	None
C4	Medication code broken		
C4.01	Medication code broken inappropriately LABEL: Medication code broken inappropriately	Medication code was broken prior to the DBL for the Week 12 analysis for no valid reason. Final decision at the DBL meeting based on medical judgment.	PPS #

Table 6.2: 1 (cont'd) Handling of iPDs

Category / Code	Description	Comments	Excluded from ¹	
D	Concomitant medication			
D1	Prohibited medication use			
D1.01	Use of restricted medication as per CTP Table 4.2.2: 1 when not provided as a rescue treatment to stabilize a worsening disease condition – prior to or up to Week 12 LABEL: Restricted medication prior to Week 12	If restricted medication is initiated during trial	PPS	#
D1.02	Use of restricted medication as per CTP Table 4.2.2: 1 when not provided as a rescue treatment to stabilize a worsening disease condition - after Week 12 LABEL: Restricted medication after Week 12	If restricted medication is initiated during trial	None	#
D2	Change in background medication			
D2.01	Any dose change in background concurrent UC treatments when not provided as a rescue treatment to stabilize a worsening disease condition – prior to or up to Week 12: Oral 5-ASA compounds LABEL: Oral 5-ASA compounds not stable	Medical review, only dose increase not used as rescue will lead to exclusion from PPS	PPS	#
D2.02	Any dose change in background concurrent UC treatments when not provided as a rescue treatment to stabilize a worsening disease condition – prior to or up to Week 12: Oral corticosteroids (incl. budesonide) LABEL: Oral corticosteroids not stable	Medical review, only dose increase not used as rescue will lead to exclusion from PPS	PPS	#

Table 6.2: 1 (cont'd) Handling of iPDs

Category / Code	Description	Comments	Excluded from ¹	
D2.03	Any dose change in background concurrent UC treatments when not provided as a rescue treatment to stabilize a worsening disease condition – prior to or up to Week 12: Azathioprine, 6-mercaptopurin or methotrexate LABEL: Azathioprine, 6-mercaptopurin or methotrexate not stable	Medical review, only dose increase not used as rescue will lead to exclusion from PPS	PPS	#

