6.6.2 Efficacy endpoints

Based on the different reasons for patients' data missing for different endpoints, various approaches will be used to assess the impact of missing data on the efficacy endpoints of this trial, depending upon the type of the endpoint. Approaches to be applied are described below.

Missing data imputations will be performed using all available on-treatment data observed up to the respective analysis cut-off date.

Binary efficacy endpoints

With regards to the handling of missing data on binary efficacy endpoints, the following table gives an overview of the proposed imputation methods which are described in more detail below.

Table 6.6.2: 1 Missing data approaches for binary efficacy endpoints

	Binary efficacy outcome observed or not	Imputation Approach Subsequent to Event of Type		Missing due to Other reasons - Withdrew consent - Loss of follow up - Data not collected - etc.
		Rescue intake	Death due to any cause	
NRI	Observed	NRI	n.a.	n.a.
	Not observed	NRI	NRI	NRI
MI	Observed	MI	n.a.	n.a.
	Not observed	MI	MI	MI
MI-NRI	Observed	NRI	n.a.	n.a.
	Not observed	NRI	NRI	MI
OC	Observed	no imputation	n.a.	n.a.
	Not observed	no imputation	no imputation	no imputation

Primary Imputation Approach – No Response Imputation [NRI]

1. If a patient takes a rescue medication (as defined in [Section 5.4.5](#)) for the treatment of ulcerative colitis or died due to any cause prior to observing the primary endpoint for this trial, then all data subsequent to the intake of such rescue will be considered to be missing.
2. For endpoints which are measured at multiple visits (thereby excluding the endpoints which are based upon the endoscopic subscore), if there are data at visits both before and after the visit with a missing outcome, then impute as success only if both neighbouring visits also represent a success (independent of whether the preceding and following observations were selected for analysis based on time windows described in [Section 6.7](#)) with no intervening use of rescue medication;

For all patients with a missing visit outcome, impute as a failure to achieve a response.

Other Imputation Approaches

- Observed cases (OC) approach: first, set all data collected after intake of a rescue medication to missing; then include all collected data with no imputation performed on the missing data. The analysis using OC approach is only based on all patients who have non-missing values in the patient set.

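### UC therapy added before week 12 but not labelled rescue leads only to exclusion from the per-protocol set, so the primary NRI analysis can count the patient as a remitter

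*SAP*

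**What the plan says.** **What counts as rescue.** Protocol Table 3.1:1 defines it as "New or increase in dose of any medication, or a surgical procedure, applied to treat new or worsening symptoms related to ulcerative colitis". The public text of SAP 5.4.5 shows one item: "Newly administered medications or surgical therapy used to treat the underlying disease UC due to disease worsening or a disease flare". Disease worsening is itself defined in Protocol Table 3.1:1 as "Worsening of clinical status or symptoms of ulcerative colitis requiring administration of rescue medication in the investigator's opinion". For patients who need extra therapy or a dose increase because of disease worsening, Protocol 4.2.1 adds: "Such patients should stay in the trial but will be considered as treatment failures in the intent-to-treat (ITT) analysis". Protocol 7.5 leaves to the SAP the detail of which rescue intakes affect the primary endpoint.

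**What is left over.** SAP Table 6.2:1, row D1.01, covers "Use of restricted medication as per CTP Table 4.2.2: 1 when not provided as a rescue treatment to stabilize a worsening disease condition", up to week 12. Rows D2.01 to D2.03 cover non-rescue dose changes in oral 5-ASA, oral corticosteroids and the permitted immunomodulators, with the comment "Medical review, only dose increase not used as rescue will lead to exclusion from PPS". The exclusion column names the PPS and nothing else.

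**How outcomes are scored.** SAP 7.4 bases the primary analysis on the RS with NRI. Under SAP 6.6.2, once a patient has taken rescue or died, "then all data subsequent to the intake of such rescue will be considered to be missing". Then: "For all patients with a missing visit outcome, impute as a failure to achieve a response". MI-NRI uses the same trigger. OC and MI also discard data only after rescue. Table 6.6.2:1 has no entry for UC medication that is not rescue.

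**The concern.** Clinical remission is meant to measure spesolimab against placebo. The plan already accepts that an outcome reached with the help of rescue should not be credited to the randomised arm. The deviation table shows that the sponsor also foresees added or increased medication outside rescue, yet the primary scoring does nothing with it. The same drug and course can therefore make one patient a failure and another a possible remitter, depending on how the reason was recorded. Clinical response and endoscopic improvement also use RS with NRI (SAP 7.5.2), so they share the gap.

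**Working it through.** **Step 1: one hypothetical patient through the rules.** SFS is 2 and RBS 2 at baseline and at week 8. The background oral steroid is then increased. Week-12 data are complete: RBS 0, mESS 1, SFS 1 (a drop of 1 from baseline).

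| Rule | Increase labelled rescue | Not labelled rescue |
|---|---|---|
| Table 6.2:1, D2.02 | does not apply | applies |
| In the RS | yes | yes |
| NRI (primary) | non-response | remission |
| MI-NRI | non-response | remission |
| OC, MI | set to missing (MI then imputes) | remission |
| PPS | not removed by D2.02 | removed |

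This does not depend on how wide rescue is. D1.01 and D2.01 to D2.03 are defined as what remains once rescue is taken out. A wider rescue definition moves patients from the right column to the left but does not change how the right column is scored.

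**Step 2: weight of one patient.** Inputs from Protocol 7.7.1: 40 per arm; remission 0.15 on placebo and 0.25, 0.30, 0.35 on low, middle and high dose; benefit threshold 0.16.

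- One patient: 1/40 = 0.025.
- Planned difference, high dose against placebo: 14/40 − 6/40 = 0.20.
- Two extra remitters on placebo: 14/40 − 8/40 = 0.15.
- Two extra on high dose: 16/40 − 6/40 = 0.25.
- Two extra on each: 16/40 − 8/40 = 0.20.
- Margin over the threshold: (0.20 − 0.16)/0.025 = 1.6 patients.

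These raw differences are only illustrative. The 0.16 criterion applies to the best-fitting dose-response model (Protocol 7.7.1, SAP 7.4).

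**Step 3: reproduce the plan's figures.** The Part 1 rule was simulated on the logit scale, with var(logit p) = 1/(n p(1 − p)) and the five candidate shapes of Protocol 7.3.1. Optimal contrasts were tested as T = c′μ̂/√(c′Vc) against the one-sided 20% max-T critical value. The significant models were then refitted by weighted least squares and the lowest AIC chosen. Success means at least one significant contrast and a maximum modelled difference of at least 0.16. With 2,000 runs against Protocol Table 7.7.1:1:

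- base case: 0.678 (stated 0.672)
- higher middle dose: 0.751 (0.746)
- sub-optimal: 0.467 (0.460)
- no effect: 0.024 (0.020)

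**Step 4: shift the rates.** The documents give no count, so an average of 1 or 2 extra remitters per 40 (0.025 or 0.05) is an assumption. The planned rates stand for the case where such patients are scored as failures. There were 1,000 runs per row; the standard error is at most about √(0.5 × 0.5/1000) = 0.016.

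| Arms with extra remitters | Success, +0.025 | Success, +0.05 |
|---|---|---|
| None (planned rates) | 0.675 | 0.675 |
| Placebo only | 0.559 | 0.487 |
| All arms equally | 0.669 | 0.678 |
| Active arms only | 0.777 | 0.845 |

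With no true effect and extra remitters on the active arms only, the chance of a significant contrast is 0.318 or 0.404 (nominal 0.20; the unshifted no-effect run gave 0.22). Success is then 0.042 or 0.087.

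**The case against.** The strongest objection is that the rescue definition cannot be read in full. SAP 5.4.5 shows one item, and SAP 7.6.4 relies on a censoring rule there that is not visible. The D2 comments presuppose that a dose increase can be rescue, although the visible item names only new medication or surgery. A reader might infer that treating persisting symptoms is never rescue under this plan. The documents do not support that: text is missing, and the protocol's disease worsening rests on the investigator's judgement, so such treatment could be labelled rescue. This limits the point to the non-rescue remainder but does not remove it.

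Second, D1.01 is not a list of non-responders given more UC therapy. It gives no reason for use, and the protocol's restriction table also covers NSAIDs, live vaccines and biologics for other diseases. That stands, and it limits the fix.

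Third, Protocol 4.2.2.1 requires stable background doses and refers in-trial use of most UC drugs to the rescue section, so what remains are deviations, which the PPS analysis removes. This helps only in part. The PPS is a sensitivity set that drops these patients on a post-randomisation event instead of scoring them, and it is analysed only at the second snapshot. Other rows of SAP Table 7.4:2 are not visible, so a further sensitivity analysis cannot be ruled out.

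Fourth, the Amendment 3 log shows that persisting symptoms were deliberately replaced by worsening symptoms in the protocol definition. That is a legitimate choice of definition, but it does not settle how the remaining cases should be scored.

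**Conclusion.** The point holds for medication that the deviation table itself classes as not rescue. On the visible rules, a week-12 outcome obtained on such therapy is scored as observed in the primary analysis, and no visible imputation method tests the effect. It can produce a remitter; it need not, because RBS 0, mESS of at most 1 and the SFS criterion must all still be met.

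The size rests on assumed counts and the planned 40 per arm. The SAP was revised for early termination; in an arm of n, each patient weighs 1/n.

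Two further inferences are tempting. One is that the gap must raise the placebo rate and work against the drug. The documents give no counts by arm or reasons for adding therapy: an excess on placebo shrinks the difference, an excess on active inflates it, and equal numbers leave success almost unchanged. The other is that two placebo patients would turn a positive Part 1 into a failure. The threshold applies to the modelled effect, a benefit of at least 0.11 but below 0.16 leads to further analysis rather than a stop (Protocol 7.7.1), and SAP Section 3 says that seamless progression to Part 2 is no longer viable.

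**What to change.** In SAP 6.6.2, under NRI and MI-NRI, score as non-response any patient who, before the week-12 assessment, has a D1.01 case involving a UC-effective drug or a D2.01 to D2.03 dose increase, as identified by blinded medical review. Leave out restricted drugs not used for UC, and the steroid uses the protocol already permits (infusion or anaphylactic reactions, adverse events unrelated to UC, local administration, return to the baseline dose after a short reduction). Keep the current rescue-only trigger as a sensitivity analysis. At minimum, add the extended scoring as a sensitivity analysis on the RS.

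Reconcile the rescue wording in Protocol Table 3.1:1, SAP 5.4.5 and the D2 comments, in particular whether new symptoms and dose increases are covered.

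The cost is a few sentences in the SAP and slightly lower observed remission rates. The cases are already flagged for manual detection. Table 6.3:1 marks deviations as not applicable at the first snapshot, so their review would have to come forward if the rule is used there. Patient care does not change.
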